Trial Design: This is a single-arm, phase I/II, study of PAC/SIR/TAC for the prevention of acute GVHD after matched related and unrelated alloHCT. First, a standard 3+3 dose escalation method will be performed combining PAC with SIR/TAC. The MTD identified during phase I, as well as serial PK/PD data, will inform the recommended phase II dose. Therefore, the recommended phase II dose will be the lowest dose that decreases the amount of pSTAT3+ CD4+ T-cells <35% at day +21 and does not exceed the MTD (see Table 1). The phase II component is powered to determine if JAK2 inhibition with PAC significantly reduces CD4+ T-cell STAT3 activation early after allogeneic HCT compared to our historical benchmark. Our published study showed the mean CD4+ T-cell STAT3 phosphorylation at day +21 was 50% among all HCT recipients, 70% for those who later developed acute GVHD, versus 32% for those who did not². Therefore, success will be defined as a reduction in CD4+ T-cell STAT3 phosphorylation to 35% or less at day +21. This phosphorylation value not only estimates biologic activity, but also falls within the standard deviation of what was observed among HCT recipients who never acquired acute GVHD². The association of CD4+ T-cell STAT3 phosphorylation and acute GVHD risk is under prospective validation, but currently offers guidance in determining the degree of on-target pathway suppression for HCT recipients on this trial. As pacritinib is a direct inhibitor of JAK2/STAT3 signal transduction, greater reduction in CD4+ T-cell pSTAT3 phosphorylation is possible in this patient population. An initial 24 patients will be treated with PAC/SIR/TAC to investigate whether the biologic activity of STAT3 in CD4+ T-cells is reduced at day +21.

Secondarily, we will monitor enrolled patients for acute GVHD by day +100. To investigate the clinical efficacy of the PAC/SIR/TAC combination in GVHD prevention, the trial will be expanded by an additional 14 subjects if 9 or less of the first 24 patients develop grade II-IV acute GVHD. This expansion threshold is based on our data from the SIR/TAC trial where the cumulative incidence of acute GVHD incidence by day +100 was 43%. PAC/SIR/TAC will be considered favorable if the primary endpoint is met AND ≤12 of the total 38 (31.6%) patients develop acute GVHD by day +100.

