An evaluable patient for the phase I portion of the trial must have either met one of the defined clinical events in the DLT definition, or if not, must have been receiving pacritinib within 72 hours of the planned day +21 blood sample for determination of pSTAT3 level. Those patients that have not had a clinical DLT event and are not actively taking pacritinib for any reason within 72 hours of day +21 will be considered not evaluable, and will be replaced.

The phase II component of this trial is designed to detect a significant change in the biologic endpoint of STAT3 activity at day +21. The preliminary data revealed that the

mean and standard deviation (SD) of CD4+ T-cell pSTAT3 activity among 18 HCT recipients at day +21 were ~50% and ~25%, respectively, regardless of acute GVHD severity. We conservatively anticipate that mean of pSTAT3 level at day +21 will decrease to 35% or less by combining PAC to SIR/TAC. With a two-sided significance level of 0.05, a total sample size of 24 will achieve 80% power to detect a decrease of 15% when the anticipated SD is 25%, which is equivalent to an effect size of 0.6. We anticipate that the actual SD will be lower than 25%. If the actual SD is 20%, the study will have 94% power to detect a difference of 15% (an effect size of 0.75).

We also aim to understand whether the observed incidence of grade II-IV acute GVHD is sufficiently promising to warrant further study in a trial adequately powered to address this clinical endpoint. Based on published and unpublished experience of over 300 treated-patients, the incidence of GVHD with SIR/TAC is 43%. We hypothesize that the cumulative incidence rate of GVHD with PAC/SIR/TAC by day +100 will reduce to 23% (a decrease of 20%) by day +100. The study expansion will be considered if 9 or less of 24 patients (37.5%) initially treated with PAC/SIR/TAC develop grade II-IV acute GVHD by day +100. The expansion will permit an additional 14 patients will be accrued.

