The expanded phase II trial (second stage of phase II) will be considered favorable if 12 or less of the total 38 (31.6%) patients develop acute GVHD by day +100. This sample size was computed using Simon's two-stage design with 10% one-sided significance level and 90% power. If this regimen is actually not effective, there is 9.8% probability of concluding that it is. If the regimen is actually effective, there is 8.6% probability of concluding that it is not. If the second stage is open (n=38), the study will achieve 95% power to detect a decrease of 15% when the SD is 25%. The Blood and Marrow Transplant Program at MCC performs approximately 190 allogeneic procedures annually. A conservative estimated accrual rate of 20% would provide at least 38 patients each year allowing for full accrual by 24 months.

An evaluable patient for primary endpoint is defined as patients who received PAC/SIR/TAC until at least day +21 of their alloHCT and who has neither relapsed nor died of any reasons without experiencing grade II-IV aGVHD until day +100. A non-evaluable PAC/SIR/TAC patient will be replaced and we anticipate 41 patients will be accrued to the interventional study in order to account for 10% of competing risks (relapse or death without GVHD) at day +100.

Additional 15 patients who receive the standard GVHD prevention regimen of SIR/TAC, will be enrolled for blood sample collection only (8 green top tubes of blood) on days +21 and +100 of the alloHCT. The amount of circulating Treg, Th1, and Th17 cells will be analyzed. The exact same eligibility criteria will apply for these subjects.

A total of up to 68 (up to 18 patients in phase I [with the 6 treated at MTD included among those analyzed in phase II] + 32 [PAC/SIR/TAC] + 3 [non-evaluable replacement] +15 [blood sample collection only]) patients will be enrolled.

Statistical analysis methods

Patient baseline characteristics will be summarized using descriptive statistics including mean, median, standard deviation and range for continuous measures and proportions and frequencies for categorical measures. As the primary endpoint of the study, one sample t-test will be employed to examine if pSTAT3 at day +21 is decreased by 15% from historic mean of 50%. A two-sided p-value of <0.05 is considered statistically

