significant. If data is not normally distributed, an appropriate transformation (i.e., logtransformation) or nonparametric test will be considered. As the key secondary endpoint, the cumulative incidence of grade II-IV acute GVHD will be estimated using the competing risk approach, where relapse and non-relapse mortality are considered the competing risks. The one-sided 90% confidence interval for grade II-IV acute GVHD will be computed using log-log transformation.

Overall and relapse-free survival (OS and RFS) will be analyzed using the Kaplan-Meier method. The association of time-to-event data with/without competing risks with other potential predictors will be explored by the Cox proportional hazards regression model and the Fine and Gray method³⁹, respectively. Fifteen patients treated with SIR/TAC alone will be enrolled for blood sample collection only on days +21 and +100 of their alloHCT. The effects of PAC/SIR/TAC versus SIR/TAC alone on Tregs, Th1, and Th17 at day +21 and +100 will be compared using the generalized linear model with identity link function, adjusting for the effect of acute GVHD (grade 0-I vs. grade II-IV). In addition, the mixed effect model will be considered to explore the difference in trends between two groups. With a two-sided significance level of 0.05, the sample size of 39 (24 in PAC/SIR/TAC and 15 in SIR/TAC) will have 84% power to detect an effect size (=difference/pooled SD) of 1 between two groups. If the second stage is open, the power will increase to 90% as the sample size of PAC/SIR/TAC increases to 38. No multiplicity adjustment will be considered for secondary and exploratory endpoints.

VI. Data collection and safety monitoring

The Data & Safety Monitoring Plan (DSMP) adopted by the H. Lee Moffitt Cancer Center & Research Institute, Inc. (MCC) will ensure that all clinical research conducted or coordinated by the Cancer Center is scientifically well designed, responsibly managed, appropriately reported and protects the rights and welfare of human participants. The methods and amount of monitoring required are dictated by the degree of risk involved to the individual participants and the complexity of the clinical research. Other entities that will assume responsibility for data and safety monitoring include:

- Principal Investigators (PI)
- The Scientific Review Committee (SRC);
- The Protocol Monitoring Committee (PMC);

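### The log-transform fallback for the primary pSTAT3 test has no reference value on its own scale; run against 50%, it would be biased toward claiming suppression

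*Combined protocol and SAP*

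**What the plan says.** Section V.7 (Statistical considerations) sizes phase II on historical data in which the "mean and standard deviation (SD) of CD4+ T-cell pSTAT3 activity among 18 HCT recipients at day +21 were ~50% and ~25%, respectively". The sample size follows from that: "With a two-sided significance level of 0.05, a total sample size of 24 will achieve 80% power to detect a decrease of 15" percentage points "when the anticipated SD is 25%, which is equivalent to an effect size of 0.6". The same section gives 94% power if the SD is 20%, and 95% power at n=38 if the second stage opens.

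Under Statistical analysis methods, a "one sample t-test will be employed to examine if pSTAT3 at day +21 is decreased by 15% from historic mean of 50" percent, with a two-sided p below 0.05 counted as significant. The fallback comes next: "If data is not normally distributed, an appropriate transformation (i.e., logtransformation) or nonparametric test will be considered". The text names no normality criterion, no rule for choosing between the two alternatives, and no reference value for either.

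The Trial Design paragraph sets a separate bar: "success will be defined as a reduction in CD4+ T-cell STAT3 phosphorylation to 35% or less at day +21".

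**The concern.** In a two-arm comparison a log or rank fallback is routine, because both arms move to the new scale together. Here one side of the comparison is a constant, and that constant is an arithmetic mean. On the log scale the test concerns the geometric mean, and a rank test concerns the median or pseudomedian. By Jensen's inequality the geometric mean of any variable data is below its arithmetic mean, so a drug with no effect still looks as if it lowered pSTAT3. The error always favours the regimen.

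The primary phase II conclusion is at stake, and meeting that endpoint is one of the two conditions for calling the regimen favourable. The choice of test would also be made after the data are seen.

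**Working it through.** **Inputs from the documents:** historic mean 50%, SD 25% (or 20%), 18 recipients; n=24 or 38; two-sided alpha 0.05; subgroup means of 32% (no acute GVHD) and 70% (acute GVHD).

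**Assumptions:** the fallback uses 50 or log(50) as its reference; the data shapes; and, where stated, a Shapiro-Wilk trigger at 5%.

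**1. The plan's own power.** For a one-sample t-test the noncentrality is effect size × √n.
- n=24, 0.6: 0.6 × √24 = 2.94, power 80.4% (plan 80%).
- n=24, 0.75: 0.75 × √24 = 3.67, power 94.0% (plan 94%).
- n=38, 0.6: 0.6 × √38 = 3.70, power 95.0% (plan 95%).

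All three reproduce, so the design was sized on the raw-scale t-test alone.

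**2. The log test with no drug effect, lognormal case.** For mean 50 and SD 25:
- log-scale variance = ln(1 + (25/50)²) = ln 1.25 = 0.223, so sigma = 0.472
- geometric mean = 50 × exp(−0.223/2) = 44.7%
- spurious standardised shift = sigma/2 = 0.236
- noncentrality = −0.236 × √24 = −1.16, or −0.236 × √38 = −1.46

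The chance of a significant decrease is then about 20% at n=24 and 29% at n=38, against a nominal 2.5%. With SD 20% it is 14.6% and 21.1%.

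**3. Other shapes, by simulation at mean 50 and SD about 25.** Entries are false significant decreases at n=24 / n=38. The mixture combines the 32% and 70% groups: a weight w on 32 with 32w + 70(1−w) = 50 gives w = 20/38 = 0.53.

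| Shape | Geometric mean | Log test always used | Log test after Shapiro-Wilk trigger | Signed-rank against 50 |
|---|---|---|---|---|
| Lognormal | 44.7 | 20% / 29% | 13-14% / 24-25% | 9% / 12% |
| Gamma | 43.9 | 18% / 29-30% | 11% / 18-19% | 6.5% / 7.6% |
| Beta(1.5, 1.5) | 41.2 | 16-17% / 31% | 4-5% / 4-10% | near nominal |
| 32/70 mixture | 41.9 | 14-18% / 27-32% | 4-7% / 4-16% | near nominal |

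In the trigger column, the low end for the last two rows comes from a stricter rule: use the log test only if Shapiro-Wilk rejects the raw data and accepts the logged data.

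**4. The raw t-test in the same settings.** Two-sided error is about 5-7%. For lognormal data the decrease tail is 5.6% at n=24 and 4.9% at n=38.

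**5. A matched reference.** With the lognormal data tested against log(50) − 0.223/2, a geometric mean of 44.7%, two-sided error returns to 5.2% at n=24 and 5.0% at n=38. The documents do not give the log-scale mean or SD needed to set this.

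**6. Adding the 35% bar.** In the lognormal case, requiring log-test significance and an observed arithmetic mean of 35% or less gives false success in 0.02% of trials at n=24. Putting the geometric mean to the bar gives 0.6% at n=24 and 0.06% at n=38.

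**The case against.** The strongest reply is that the plan never says the fallback would be run against 50. The historic mean is attached to the t-test; the fallback is only to be considered, and the transformation must be appropriate. The historical data come from the team's own published study, so a matched log-scale reference may be within reach, and step 5 shows it would cure the problem. This stands as a limit on the claim. It does not remove the concern, because the plan neither supplies such a reference nor commits to deriving one.

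The trigger also matters. Applying the log test to every trial ignores the condition that the data be non-normal, and for bounded or mixture shapes a trigger removes much or nearly all of the inflation. The shapes that stay inflated are imperfect models of a percentage: lognormal and gamma with mean 50 and SD 25 each put about 4% of patients above 100%. The plan also expects an SD below 25%, which reduces the bias. All of this stands and is reflected in the ranges.

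The 35% success bar would make false success rare if the observed arithmetic mean also had to clear it. However, Statistical analysis methods defines significance by p<0.05 against 50% and does not state the bar as a joint condition. The power figures match the test alone: if the true mean were 35%, requiring an observed mean of 35% or less would cut power to about 50%. The bar therefore cannot be taken as a safeguard already in the plan.

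**Conclusion.** The concern holds conditionally and should be fixed; it is not a fatal flaw. If the log fallback is run against log(50), it tests the wrong quantity and favours a finding of suppression. Over the assumed shapes with mean 50% and SD 25%, the false significant decrease is about 14-20% (n=24) and 27-32% (n=38) if the log test is always used. After a Shapiro-Wilk trigger it is about 11-14% and 18-25% for right-skewed shapes, and about 4-7% and 4-16% for bounded or mixture shapes.

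A reader might infer that the plan as written carries a false-positive rate near 30% through either fallback. The documents do not support that. The comparator, trigger and data shape are unstated. Rates near 30% arise only for the log test, at n=38, with SD 25% and no trigger. The signed-rank test stays at about 2-12% and is nominal when the data are symmetric about 50. Nor do these figures describe false success if the 35% bar is applied jointly to the observed mean.

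**What to change.** In Statistical analysis methods, keep the one-sample t-test on the raw percentage scale as the primary analysis whatever the shape of the data, with a bootstrap confidence interval for the mean as sensitivity. Allow a log or rank analysis only as supportive, against a geometric mean or median re-derived from the 18 historical values. State in the same place whether an observed mean of 35% or less is required in addition to p<0.05.

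The main change is about one sentence. The cost is a slight loss of efficiency, and two-sided error of about 6-7% instead of 5%, if the data are strongly right-skewed. Naming a trigger, a choice rule and a matched reference would also remove the bias, but it needs the log-scale summary of the historical data before the trial data are examined.

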Naïve CD4+ T cells are plastic and may develop into various functional phenotypes (Th1, Th2, Th17, Treq) through specific cytokine-mediated intracellular signaling events. Th17 cells are implicated in murine and human GVHD^{2,16,17}. IL-6 mediates Th17 development by activating JAK2/STAT3 and influencing the expression of RORgammaT¹⁸. Conversely, IL-2 signaling through STAT5 favors Foxp3 expression and subsequent immune tolerizing Treg development¹⁹. Studies in murine acute GVHD have shown that mice transplanted with CD4+ T cells deficient in IL-17 have significantly reduced mortality²⁰. We and others have demonstrated that tissue invading Th17 cells are significantly increased at time of acute GVHD diagnosis in humans as well². Additionally, we have demonstrated that increased tissue-resident Th17 cells correlates with GVHD severity and portends a poor response to upfront therapy with glucocorticoids (Figure 1A)². Deletion of STAT3 in donor T-cells favors Treq development and improves the survival of transplanted mice²¹. We have shown that CD4+ T-cell STAT3 activation by IL-6 is significantly increased early after allogeneic HCT among asymptomatic patients who later develop grade II-IV acute GVHD (Figure 1B,C)². This observation uniquely identified JAK2 and downstream STAT3 as clinically dynamic, druggable targets in acute GVHD. The degree of IL-6-induced CD4+ T-cell STAT3 phosphorylation was 11% for healthy non-transplant controls, 32% for those who did not develop acute GVHD, and 70% for recipients who did develop acute GVHD by day +100. This trial biologically targets JAK2/STAT3 activation by combining pacritinib, a selective JAK2 inhibitor, with SIR/TAC to reduce the CD4+ T-cell STAT3 phosphorylation to at least 35%. This target coincides with the STAT3 phosphorylation range observed among HCT recipients who did not develop acute GVHD in our prior exploratory study. The association of CD4+ T-cell STAT3 phosphorylation and acute GVHD risk is under prospective validation, but currently offers guidance in determining the degree of on-target pathway suppression for HCT recipients on this trial. We will strengthen our current investigation by determining if JAK2/STAT3 pathway suppression reduces the cumulative incidence of acute GVHD. The trial will be expanded by 17 patients to study the effect of PAC/SIR/TAC on GVHD prevention, if 9 or less of the 24 initial patients develop acute GVHD by day +100.

[figure not shown]
[figure not shown]

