Pacritinib dose at day +69	Day +70 reduction	Day +84 reduction
200mg BID	200mg daily	100mg daily
200mg daily	100mg daily	100mg every other day (QOD)
100mg daily	100mg QOD	100mg on Sunday and

^{*} Patients demonstrating signs/symptoms of heart failure on PAC/SIR/TAC will undergo a 2-D echocardiogram to document the left ventricular ejection fraction. Subsequent echocardiograms will be performed per the discretion of the attending physician based on clinical need.

T ,
Linursday
Tharbady

II. Trial objectives

- a. Primary objectives:
- i. Phase I: Determine the lowest biologically active dose of pacritinib that is safe and well tolerated when combined with SIR/TAC.
- ii. Phase II: Determine if PAC/SIR/TAC suppresses STAT3 activity in circulating CD4+ T-cells at day +21², to at least 35% phosphorylation.

.

- b. Secondary objectives:
 - i. Investigate whether PAC/SIR/TAC reduces the cumulative incidence of acute GVHD by day +100, compared to our published rate of 43% from SIR/TAC alone. This benchmark is bolstered by an ongoing retrospective analysis of 819 patients treated with SIR/TAC, MTX/TAC, or MMF/TAC, where the incidence of acute GVHD with SIR/TAC was similar to rates observed in our trial.
 - ii. Study the effect of PAC/SIR/TAC on Treg, Th1, and Th17 differentiation among circulating T-cells at day +21 and day +100.
 - a) A subset of 15 patients treated with standard SIR/TAC alone who are receiving a matched related or unrelated alloHCT will also be enrolled for blood sample collections only on day +21 and day +100.
 - b) The effects of PAC/SIR/TAC versus SIR/TAC on Treg, Th1, and Th17 development will be investigated.
 - iii. Determine how PAC/SIR/TAC impacts CD28 and IL-2 receptor signal transduction by measuring S6 (mTOR), H3 ser10 (Aurora kinase), and STAT5 phosphorylation in CD4+ T-cells at days +21 and +100. Phosphoprotein values will be compared to SIR/TAC only patients (n=15) enrolled in the sample-only portion of the trial.

III. Trial endpoints

- a. Primary endpoints:
 - i. Phase I: The lowest biologically active dose of PAC that is safe and well tolerated with SIR/TAC
 - ii. Phase II: STAT3 activity in circulating CD4+ T-cells at day +21².
- b. Secondary endpoints (phase II only):
 - i. Cumulative incidence of acute GVHD by day +100
 - ii. Treg, Th1, and Th17 differentiation among circulating T-cells at day +21 and day +100.

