Phase I: The lowest biologically active dose of PAC that is safe and well tolerated with SIR/TAC

Phase II: STAT3 activity in circulating CD4+ T-cells at day +212

8 green top tubes will be collected at baseline (day -30 to -5), day +21, and day +100. This is equivalent to 5.5 tablespoons of blood for each assessment. Peripheral blood mononuclear cells (PBMC) will be isolated by Ficoll density gradient. PBMCs will be stimulated with IL-6 for 20 minutes to activate STAT3. Phosphoproteins will be analyzed within T-cells by flow cytometry as described².

Secondary Endpoints

1. Cumulative incidence of acute GVHD³⁸ by day +100

Acute GVHD severity grading and monitoring:

Patients will be monitored for clinical signs of acute GVHD. Acute GVHD will be graded per the 1995 consensus guidelines.²⁷ (see Appendix A).

Therapy for established acute GVHD:

This protocol does not dictate any one specific therapy for acute GVHD. The primary physician may direct the management of acute GVHD per their discretion and in accordance with MCC standard practice.

2. Treg, Th1, and Th17 differentiation among circulating T-cells at day +21 and day +100

Treg and Th1 will be analyzed by flow cytometry. Treg will be identified by expression of CD4, bright CD25, lack of CD127, and intracellular expression of Foxp3. Th1 will be identified by expression of CD4+, and intracellular T-bet+ and IFN-gamma+ [post PMA/ionomycin stimulation]. Th17 differentiation will be assessed functionally by IL-17 Elispot using PBMCs on day +21 and day +100. IL-17 Elispot is preferred to analyze Th17 as the anticipated frequency of circulating Th17 in the periphery is low post allogeneic HCT. Treg and Th17 will be evaluated at baseline, day +21, and day +100. A subset of 15 patients treated with SIR/TAC alone per Moffitt standard practice will be enrolled for blood sample collection only on days +21 and +100 of their alloHCT. The effects of PAC/SIR/TAC versus SIR/TAC alone on Tregs, Th1, and Th17 will be compared among the two groups.

3. CD28 and IL-2 signal transduction assessment by S6, H3 ser10, and STAT5 phosphorylation in CD4+ T-cells at days +21 and +100

Steady-state mTOR and Aurora kinase activity (S6 and Histone 3 ser10, respectively) and IL-2 mediated STAT5 activity will be evaluated at baseline, day +21, and day +100. Phosphoproteins will be analyzed within T-cells by flow cytometry as described².

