- 4. Pharmacokinetic (PK) parameters: For all patients enrolled in the phase I portion of this study, pharmacokinetic sampling of plasma pacritinib levels will be drawn on days 0 and +21 at the following time points: pre-dose, +4 hours, +12 hours, and +24 hours.
- Analysis of tissue-infiltrating immune cell subsets: We will obtain available GVHD target organ (e.g. skin, liver, GI) biopsy samples to study tissue-infiltrating CD4 T cell subsets (Th1, Th2, Th17, Treq) through tissue IHC (immunohistochemistry). These biopsies were obtained as part of routine clinical practice for GVHD diagnosis, and these available resources only will be used for this purpose (i.e. no clinical trial-specific biopsies will be obtained). At time of this protocol amendment when trial accrual is now complete, we expect approximately 25 total representative samples (respecting biopsy samples from skin, and GI sites including gastric, duodenal, and rectum) available to be included in this analysis. We will also enlist 25 representative historical control subject GVHD biopsy samples for comparison, arising from patients previously treated with standard of care sirolimus/tacrolimus GVHD prevention off-protocol. These will also be obtained from existing historical biopsy samples (no new biopsies to be performed). From these available biopsy samples, slides will be prepared, tissue stained for Thsubset markers (CD4/Tbet, CD4/GATA3, CD4/RORy, and CD4/FoxP3), and data acquired in collaboration with the Moffitt Pathology department, Tissue/Histology Core, and Image Analysis Core. Statistical comparisons will be made across pacritinib trialtreated subjects vs. standard of care off-protocol subjects to discern any differences. Other variables considered in this analysis will include clinical GVHD stage, time from transplant, and pathologic GVHD grade.

7. Statistical considerations

Clinical trial design, power calculations, and analysis

Phase I consists of a standard 3+3 design with three PAC dose cohorts. The DLT definitions are described on page 9 of this protocol. The MTD is defined as the highest dose level at which one or none of 6 subjects develop a DLT, and the combination of safety and biologic activity of pacritinib will dictate selection of recommended phase II dose. A total of 12-18 patients will be enrolled to determine the PAC MTD. Patients treated at the MTD (or lowest biologically active dose) in phase I will be analyzed among those treated in phase II.

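### The Treg/Th1/Th17 group comparison adjusts for acute GVHD, an outcome the regimen is expected to change, over an unstated window

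*Combined protocol and SAP*

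**What the plan says.** The secondary objective on T-cell subsets (section II, item ii(b)) reads: "The effects of PAC/SIR/TAC versus SIR/TAC on Treg, Th1, and Th17 development will be investigated". Section V.6, Secondary Endpoints, describes a plain two-group contrast: "The effects of PAC/SIR/TAC versus SIR/TAC alone on Tregs, Th1, and Th17 will be compared among the two groups". Neither place asks for an effect at fixed GVHD status.

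The paragraph on statistical analysis methods in section V.7 then fits a generalized linear model with an identity link at days +21 and +100, "adjusting for the effect of acute GVHD (grade 0-I vs. grade II-IV". A mixed model is mentioned only as a possible exploration of trends, and its covariates are not listed. No unadjusted comparison or sensitivity analysis is named. The same paragraph states 84% power for 24 vs 15 patients and 90% for 38 vs 15, at an effect size of 1.

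On GVHD itself, section V.7 gives 43% on SIR/TAC and continues: "We hypothesize that the cumulative incidence rate of GVHD with PAC/SIR/TAC by day +100 will reduce to 23"%. Grade II-IV acute GVHD is also the key secondary endpoint. The adjustment sentence gives no time window for it. The Study Calendar (Appendix D) captures GVHD in four intervals running to day +130.

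**The concern.** Acute GVHD is not a baseline factor here. It develops after pacritinib starts on day 0, and the regimen is designed to reduce it. If the regimen changes GVHD and the marker is related to GVHD, the arm coefficient from the adjusted model is not the effect of the regimen on the marker.

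- **Day +100.** GVHD may lie on the path from regimen to marker, so adjusting removes part of the effect.
- **Day +21.** If the covariate is GVHD up to day +100, the model conditions on events that can follow the blood sample and may be a consequence of the marker.

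The first condition is the protocol's hypothesis. The second is part of its rationale, although the patient evidence is from tissue: "tissue invading Th17 cells are significantly increased at time of acute GVHD diagnosis in humans". At stake is the one main model for this secondary objective. Two analysts could also fit different models from the same sentence, because the window is open. The pSTAT3 primary test and the rule for calling the regimen favourable do not use this model.

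**Working it through.** **1. The stated power.** Two-sample t-test, two-sided 0.05, d = 1, noncentrality d / √(1/n₁ + 1/n₂).

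- 24 vs 15: standard error √(1/24 + 1/15) = 0.329 SD, noncentrality 3.04, power 84.1% (stated 84%).
- 38 vs 15: standard error √(1/38 + 1/15) = 0.305 SD, noncentrality 3.28, power 89.6% (stated 90%).

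The stated figures are reproduced with no covariate, so they describe the unadjusted contrast and not the planned model.

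**2. The shift in the coefficient.** Write marker = τ·arm + g·GVHD + error, with GVHD rates of 23% and 43%. The total regimen effect is τ + g(0.23 − 0.43) = τ − 0.20g. The GVHD-adjusted coefficient is τ, that is, total + 0.20g. For |g| = 0.5 to 0.8 SD the shift is 0.20 × 0.5 = 0.10 to 0.20 × 0.8 = 0.16 SD. It is towards zero when a worse marker goes with more GVHD and away from zero when the relation is reversed. If the two GVHD rates are equal, it is zero.

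The gap g is an assumption. The documents give no blood subset values by GVHD status, and section V.6 says "the anticipated frequency of circulating Th17 in the periphery is low post allogeneic HCT".

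**3. Simulation of the adjusted model.** 20,000 trials per setting; normal marker with SD 1; true effect 1 SD. Except in the mediator row, GVHD follows a logistic model given the marker. Each pair is for a gap of 0.5 / 0.8 SD.

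| Setting | 38 vs 15: estimate; power | 24 vs 15: estimate; power |
|---|---|---|
| GVHD 43% vs 23% | 0.899 / 0.837; 81.9% / 80.3% | 0.897 / 0.838; 74.5% / 72.8% |
| Mediator model, day +100, 43% vs 23% | 0.896 / 0.841; 82.1% / 81.3% | 0.900 / 0.840; 75.0% / 73.7% |
| Regimen lowers GVHD only through the marker (to 31% / 25%) | 0.939 / 0.858; 86.3% / 82.5% | 0.941 / 0.856; 79.9% / 75.3% |
| GVHD status at day +21 sampling, assumed 10% vs 5% | 0.976 / 0.959; 87.4% / 87.2% | 0.974 / 0.961; 81.2% / 81.4% |
| Marker-GVHD sign reversed, 43% vs 23% | 1.100 / 1.162 | 1.101 / 1.158 |
| GVHD 43% in both arms | 1.00; 90.8% / 93.4% | 1.00; 85.1% / 88.7% |

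With no true marker effect and GVHD at 43% vs 23%, the adjusted test rejects in 6.4% / 8.5% of trials (38 vs 15) and 5.9% / 7.6% (24 vs 15). The unadjusted test rejects in 4.8-5.0%. This null case needs the regimen to act on GVHD by a route that bypasses the marker (odds ratio 0.38 / 0.34).

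**4. Bias and collinearity.** With no marker-GVHD relation (g = 0) but GVHD still at 43% vs 23%, the adjusted model has about 81% power (24 vs 15) and 88% (38 vs 15). So about 2 to 3 of the 8 to 11 points lost in the first row come from carrying a covariate correlated with arm, and the rest from the shift.

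**The case against.** The strongest case against acting is that the effect is small and its main input is assumed. A shift of 0.10 to 0.16 SD is about a third to a half of the standard error (0.33 or 0.30 SD). It sits in a secondary, non-randomized comparison with 15 controls and no multiplicity adjustment. Three subsets at two times make six tests; if these were independent, the chance of at least one false positive would already be 1 − 0.95⁶, about 26%. The sign is uncertain too, particularly at day +100, after GVHD treatment that the protocol leaves open: "The primary physician may direct the management of acute GVHD per their discretion". Day +100 is the natural reading of the GVHD window, since the endpoint is defined that way elsewhere. The unadjusted difference is itself open to confounding. And with recruitment finished ("At time of this protocol amendment when trial accrual is now complete"), replacing the one prespecified model could look data-driven; adding the unadjusted result beside it would inform readers equally well.

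Much of this stands. The size is modest and conditional, the direction cannot be asserted, and any change must be dated. The rest does not rescue the model. Reading the window as day +100 makes the day +21 analysis condition on later events. Adjusting for GVHD does not repair confounding by pre-transplant factors. The choice of main model is more than preference, because the objective, the endpoint description and the power statement all describe the contrast without GVHD.

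**Conclusion.** The concern holds. The only main model for Treg, Th1 and Th17 targets a quantity that no objective asks for, and its covariate has no stated window. Those two points rest on the text alone.

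The size rests on an assumed gap of 0.5 to 0.8 SD by GVHD status and on the protocol's 43% vs 23%. A true 1 SD effect is then estimated as 0.84 to 0.90 SD, or as 1.10 to 1.16 SD if the marker-GVHD relation runs the other way, and the false-positive rate is 6-9% against 5%. The distortion is smaller if the regimen acts on GVHD only through the marker or if GVHD status at day +21 sampling is used. It vanishes if the regimen leaves GVHD unchanged or the marker is unrelated to GVHD. Gaps above 0.8 SD would distort more but need implausible direct effects of the regimen on GVHD, so nothing is claimed for them. The plan should be changed, but the primary conclusion is not at risk.

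**What to change.** In section V.7, under statistical analysis methods:

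1. Make the PAC/SIR/TAC vs SIR/TAC comparison without a GVHD term the main analysis at days +21 and +100. This is the contrast that the 84% and 90% power figures describe.
2. Optionally adjust for pre-transplant factors, such as donor type and conditioning regimen, where both groups have them.
3. Report the GVHD-adjusted model beside it as exploratory, and state its window: onset before the sample, or onset to day +100.
4. State whether the mixed model carries a GVHD term.
5. Because accrual is complete, date the change and report both results, so that the new main model does not appear to have been chosen from the data.

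The cost is one or two sentences and no new data. If GVHD turns out equal at 43% in both arms, dropping the term gives up a little precision: power of 90% instead of 91-93% (38 vs 15), and 84% instead of 85-89% (24 vs 15). Neither model removes confounding from the non-randomized controls, and the report should say so.
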